9.3.1.1 Relationship Assessment

For the purpose of this observational study, only AEs related to the collection of additional endoscopy biopsy will be reportable and by definition will always be assessed as related. The degree of certainty about causality will be graded using the 2 categories below.

- **Definitely Related:** There is clear evidence to suggest a causal relationship, and other possible contributing factors can be ruled out. The clinical event, including an abnormal laboratory test result, occurs within a reasonable timeframe after study procedure(s) and cannot be explained by concurrent disease or other drugs or chemicals.
- **Possibly Related:** There is some evidence to suggest a causal relationship (e.g., the event occurred within a reasonable time after study procedure(s)). However, the influence of other factors may have contributed to the event (e.g., the subject's clinical condition, other concomitant events). Although an adverse event may be judged only as "possibly related" soon after discovery, it can be flagged as requiring more information and later be upgraded to "probably related" or "definitely related", as appropriate.

9.3.1.2 Recording/Documentation

All reportable adverse events that are identified will be recorded on an appropriate case report form (CRF). AEs developing within 3 days after the SOC endoscopy in subjects who consented to collection of extra research biopsies during SOC endoscopy procedure will be considered. All reported adverse events will be classified using the Common Terminology Criteria for Adverse Events (CTCAE) developed and maintained by CTEP at National Cancer Institute.

9.3.2 Reporting Pregnancy

A pregnancy will not be reported as an AE and is not an exclusionary condition for this observational study. However, pregnancy may prohibit participants from performing certain SOC procedures.

9.3.3 Analysis/Management

The incidence of AEs is expected to be low in this observational study; therefore, the primary analysis of AEs will occur by the medical monitor as described in Section 9.4.1 **Error! Reference source not found.** Additional management is not expected to be necessary.

9.4 Reporting Procedures

As this study is a low risk nonintervention study, safety data will not be reviewed by the National Institute of Allergy and Infectious Diseases (NIAID) Data and Safety Monitoring Board or the Safety Monitoring Committee. The safety oversight will be conducted by the principal investigator and the NIAID Medical Monitor.

9.4.1 NIAID Medical Monitor Review

Upon entry of a serious adverse event, the DMCC created Adverse Event Data Management System (AEDAMS) will immediately notify the, site PIs, the NIAID Medical Officer (MO), of any reported adverse events via email.

Serious adverse events will be reviewed by The NIAID Medical Officer (MO) within 2 business days after notification by the DMCC via AEDAMS. A back-up notification system is in place so that any delays in review by the MO beyond a specified period of time are forwarded to a secondary reviewer. Cumulative reports of AEs and SAEs will be reviewed at a minimum of every 6 to 12 months.

Non-serious expected adverse events: Except those listed above as immediately reportable, non-serious expected adverse events that are reported to or observed by the investigator or a member of his/her research team will be submitted to the DMCC in a timely fashion (within 20 working days).

The DMCC will post aggregate reports of all reported adverse events for review by NIAID Medical Officer and Project Manager

9.4.2 Notifying the Institutional Review Board

SAEs will be reported to regulatory authorities per applicable federal regulations and institutional policy by the site principal investigator. Adverse events will be reported, in summary form, at the time of continuing annual review to the IRB.

9.4.3 Reporting Timeline

Requirements for reporting SAEs for this observational study are as follows:

- Within 24 hours (of learning of the event), investigators must report any reportable Serious Adverse Event (SAE) that:
 - Is considered life-threatening/disabling or results in death of subject
 - OR-
 - Is Unexpected/Unanticipated
- Investigators must report all other reportable SAEs within 5 working days (of learning of the event).
- All other (suspected) reportable AEs must be reported to the RDCRN within 20 working days of the notification of the event or of the site becoming aware of the event.
- Investigators will forward all safety reports and related communications to the IRB within 15 days of receipt.
- A summary of all adverse events will be reported to the IRB with a continuing review submission.

9.5 Type and Duration of the Follow-up of Participants after Adverse Events

Subjects experiencing adverse events **due to research-related activities will be followed until:**

- a) the AE resolves
- b) the participant is stable

9.6 Participant Discontinuation

Participants may choose to withdraw from the observational study at any time, during a SOC visit, or afterwards in person, by telephone, or in writing.

Participants may be prematurely terminated from the observational study for the following reasons:

1. The participant elects to withdraw consent from all future observational study activities.
2. The participant is "lost to follow-up" (i.e., no further follow-up is possible because attempts to re-establish contact with the participant have failed).
3. The investigator no longer believes participation is in the best interest of the participant.

10 Protocol Deviations

10.1 Protocol Deviation Definitions

10.1.1. Protocol Deviation

The investigators and site staff will conduct the study in accordance to the protocol; no deviations from the protocol are permitted. Any change, divergence, or departure from the study design or procedures constitutes a protocol deviation. As a result of any deviation, corrective actions will be developed by the site and implemented promptly.

10.1.2. Major Protocol Deviation (Protocol Violation)

A Protocol Violation is a deviation from the IRB approved protocol that may affect the subject's rights, safety, or well-being and/or the completeness, accuracy and reliability of the study data. In addition, protocol violations include willful or knowing breaches of human subject protection regulations, or policies, any action that is inconsistent with the NIH Human Research Protection Program's research, medical, and ethical principles, and a serious or continuing noncompliance with federal, state, local or institutional human subject protection regulations, policies, or procedures.

10.1.3. Non-Major Protocol Deviation

A non-major protocol deviation is any change, divergence, or departure from the study design or procedures of a research protocol that does not have a major impact on the subject's rights, safety or well-being, or the completeness, accuracy and reliability of the study data.

10.1.4. Reporting and Managing Protocol Deviations

The study site principal investigator has the responsibility to identify, document and report protocol deviations as directed by the study Sponsor. However, protocol deviations may also be identified during site monitoring visits or during other forms of study conduct review.

Upon determination that a protocol deviation (major or minor) has occurred, the study staff will a) notify the site Principal Investigator, b) notify the DMCC and c) will complete a Protocol Deviation form. The Protocol Deviation form will document at a minimum the date PD occurred, the date PD identified, a description of event, whether the deviation resulted in SAE/AE, the signature of PI, report to central IRB, and documentation of a corrective action plan. The DMCC and DAIT/NIAID may request discussion with the PI to determine the effect of the protocol deviation on the study participant and his/her further study participation, the effect of the protocol deviation on the overall study, and corrective actions. The PI will complete and sign the Protocol Deviation form and submit it to the DMCC and to the central IRB, per IRB regulations. Major protocol deviations will be reported to the SMC by the NIAID Medical Monitor at the Medical Monitor's discretion.

11 Clinical Monitoring Structure

11.1 Site Monitoring Plan

Clinical site monitoring will be conducted according to the Safety Monitoring Plan (SMP) to ensure that human subject protection, observational procedures, and laboratory and data collection processes are of high quality and meet sponsor, ICH, Good Clinical Practice, and regulatory guidelines. Representatives from the DMCC and/or NIAID will visit each clinical site or meet with each clinical site via telephone during a specified timeframe according to the Project 1 CMP. Key study personnel must be available to assist the visitors during these visits or attend the call if completed via telephone. Additional details regarding clinical site monitoring, including remote monitoring, are outlined in the Project 1 CMP and MOO.

12 Statistical Considerations

12.1 Description of the Analyses

Through the use of a large sample of prospective clinical data collected in a standardized way, this research aims to eventually develop novel COMs that will provide new paradigms to diagnose, treat, and monitor subjects with EoE, EG and EC. The current protocol focuses on examining the correlation of COMs, histology and molecular transcriptome as well as the longitudinal profile of these variables. The analysis plans discussed in this section should give us clues to narrow down COMs for developing composite scores for each disease entity in future studies. Analysis for Aim I will be conducted by senior statisticians, Drs. [name] and [name]. Analysis for Aim II will be conducted by cytogenetic statisticians, Drs. [name] and [name].

12.2 Appropriate Methods and Timing for Analyzing Outcome Measures

This is an observational study. No interim analysis for early conclusion of the study is planned.

12.3 Addressing Study Objectives

This study can be appropriately deemed as an early phase study of developing innovative tools for diagnosis and monitoring clinical outcomes. The current protocol is more exploratory in nature as opposed to validation of the tool, focusing on correlation between phenotypes, histology and genetic biomarkers. Aim 1 is determine the correlation of EoE, EG, and EC clinical outcome measures (COMs) with mucosal eosinophilia, while Aim 2 is to determine the correlation of the molecular profile for EoE, EG, and EC with clinical outcome measures (COMs) and mucosal eosinophilia. With the analyses discussed in 11.6, we hope to identify a set of variables that can be used to develop a composite score for EoE, EG, and EC respectively for further validation.

12.4 Sample Size Consideration

We aim to enroll 600 EoE, 300 EG, and 150 EC patients in the trial between all participating sites. This sample size will provide at least 80% power to detect a true correlation of 0.26 in the EC patients, 0.17 in the EG patients, and 0.14 in the EoE patients (Table 3). This sample size will also provide at least 80% power to detect disease group effect sizes of at least 0.35 when comparing phenotypic and clinical outcomes among disease groups. Based on the sample size numbers provided from each, after taking attrition into account, we anticipate more than an adequate sample size to reach power of 80% with $\alpha=0.01$ when assuming an adjustment for 6 covariates within each disease (EoE, EG, EC), even if the correlation of eosinophil peak and clinical outcome measures is low. These ~1,000 patients will allow for some subgroup analyses to explore consistency of effects within subgroups (e.g. adults versus pediatrics, newly diagnosed versus previously). Patients will be enrolled so that they can be followed for a minimum of one year. Up to 1200 patients may be enrolled to reach the target number of 1050.

Table 3. Intradisease Correlations

Sample Size	Detectable Increase in R ²	Corresponding Correlation (R) (adjustment for covariates)	Correlation (no adjustment)
100	0.10	0.32	0.33
150	0.07	0.26	0.27
200	0.05	0.22	0.24
300	0.03	0.17	0.20
400	0.03	0.17	0.17
600	0.02	0.14	0.14

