Pediatric EoE Symptom Score (PEESS)- PEESV2.0 is a pediatric PRO that contains patient and parent proxy instruments that can be easily understood. Scoring is based on two domains that evaluate frequency and severity of the symptoms reported by the patient (see Appendix). PEESV2.0 will be used to assess EoE symptoms. In addition, the PEESV2.0 will be used to assess pediatric EG as symptoms are similar to those present in EoE.

EoE Symptom Activity Index (EEsAI)- The EEsAI is an adult symptom module that has been content and face validated and represents an EoE-specific PRO. The EoE-QOL is an adult 37 item, 5 factor HRQL specific for adult EoE that has demonstrated excellent internal consistency.

Likert dyspepsia scale- Since no instruments are available to date for pediatric EG, we will use the Likert dyspepsia scale as an instrument to assess for related health.

Severity of Dyspepsia Assessment (SODA)- Since instruments are not available to date for adult EG, we will use the severity of dyspepsia assessment (SODA) scale as a validated instrument to assess dyspepsia related health.

Pediatric Ulcerative Colitis Activity Index (PUCAI)- The PUCAI is a validated pediatric objective measure used to standardize reporting of clinical ulcerative colitis activity. The index is composed of a 6-point scale that includes abdominal pain, rectal bleeding, stool consistency, number of stools, nocturnal stools and activity level. Scores range from 0-85 with a score of 45 being used for most studies indicating disease activity.

Simple Clinical Colitis Activity Index (SCCAI)- The SCCAI is a validated symptom based index (score 0–19) used to assess ulcerative colitis. It shows good correlation with other measures of ulcerative colitis disease activity. The SCCAI will be used to assess adult EC as symptoms are similar to those present in EC.

PedsQL™ 3.0- This instrument is a disease-specific measure of health-related quality of life for pediatric patients diagnosed with EoE.

EoE-QoL-A- The EoE-QoL-A is a self-reported questionnaire designed to assess disease-specific health related quality of life in adult EoE patients. Questions are designed to evaluate established domains of Health Related QOL, such as social functioning, emotional functioning, and disease impact on daily life experiences. It is a 37-item measure with five subscales: eating/dietary impact, social impact, emotional impact, disease anxiety and choking anxiety.

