12.5 Final analysis plan

The research study will be explained in lay terms to each potential research participant. The potential participant will sign an informed consent form before undergoing any study procedures. Once the informed consent has been signed, the participant is considered enrolled in the study and will be assigned a unique participant number. Each enrolled subject becomes part of the longitudinal study.

AIM 1: We will perform intergroup and intragroup baseline analysis at study entry, longitudinal analysis, and supportive and exploratory analysis with the expertise of our statisticians Drs. [name] and [name]. To describe the clinical profile for each disease entity, separate analysis will be performed at baseline for participants in the newly diagnosed cohort and the previously

diagnosed (ongoing cohort). Summary statistics, grouped by adults or children, will be calculated for the demographic and the outcome variables. Differences in these phenotypic variables between EoE, EG, and EC will be tested using ANOVA or chi square tests. To evaluate the correlation of peak eosinophils with COMs (e.g. PROs, EREFS, QoL metrics), multivariate regression analysis will be conducted separately for each COM, with the COM serving as the dependent variable and peak eosinophil counts as the independent variable. Covariates in the model will include, but are not limited to, sex, age group, atopic disease, race, disease duration, and medication usage. To assess the difference in the extent of this correlation between cohorts or age groups, an interaction term of peak eosinophil counts by the selected categorical variable will be introduced to and tested under the above model. Similarly, PROs will be correlated with the other endoscopy (EREFs, Lanza score, UCCIS) and histology (biopsy evaluation forms) measures using the same approach. The normality assumptions will be evaluated, and transformations will be used (e.g. square root, log, rank) as appropriate. The correlation analyses discussed above will be conducted separately for EoE, EG, and EC.

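### The 80% power claim uses each disease's full sample, but every symptom and quality-of-life measure is used in one age group only, so no such analysis has that n or can fit the adult/child terms

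*Protocol*

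**What the plan says.** Protocol section 12.4 sets the enrolment: "We aim to enroll 600 EoE, 300 EG, and 150 EC patients in the trial between all participating sites". It then states the power: "This sample size will provide at least 80% power to detect a true correlation of 0.26 in the EC patients", with "0.17 in the EG patients, and 0.14 in the EoE patients (Table 3"). The conditions are given as "reach power of 80% with $\alpha=0.01$ when assuming an adjustment for 6 covariates within each disease (EoE, EG, EC"). Table 3 lists, by sample size, the smallest R² increment that can be detected, its square root as an adjusted correlation, and an unadjusted correlation. The stated values are the adjusted entries at n = 150, 300 and 600.

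Section 12.5 sets the analysis: "multivariate regression analysis will be conducted separately for each COM", with the COM as outcome, peak eosinophil count as predictor, and each disease analysed separately. Age group is among the listed covariates. For comparing the association by cohort or by age group, the section plans this: "an interaction term of peak eosinophil counts by the selected categorical variable will be introduced to and tested under the above model". The only age grouping that section names is adults versus children, in its sentence on summary statistics. The one-year change models use the same covariates.

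Table 1 in section 4.2.1 marks each symptom and QoL row Peds, Parent or Adult. Only the endoscopy, histology and transcriptome rows are marked Both. The text below the table agrees; for example, "The SCCAI will be used to assess adult EC", while PUCAI is the paediatric index.

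**The concern.** The power statement and the model specification do not describe the same analyses. A regression on SCCAI contains only adults with EC, and a regression on PUCAI only children with EC; neither can contain 150 patients. The same holds for Likert dyspepsia and SODA in EG, for PEESS and EEsAI or PedsQL and EoE-QoL-A in EoE, and for the two PROMIS forms in all three diseases. PedsQL is divided again by age band and reporter.

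In any of these models an adult/child indicator takes a single value. It cannot serve as a covariate, and its interaction with eosinophil count cannot be tested.

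Symptom and QoL scores are named in the primary objective together with endoscopy. A reader of section 12.4 would take a null result for one of them as coming from an analysis with 80% power at a low correlation. A reader of section 12.5 would expect an age-group comparison that cannot be produced for them.

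**Working it through.** **Inputs from the protocol.** n = 600 / 300 / 150 (EoE / EG / EC); alpha 0.01; power 80%; 6 covariates; stated R = 0.14 / 0.17 / 0.26 (section 12.4). One model per COM and disease (section 12.5). Age assignment of each measure (Table 1).

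**Assumptions, not in the protocol.** Two-sided test. Covariate R² (R²c) of 0.10, chosen because it reproduces the R² column of Table 3. One age group's share of a disease sample: 50%, with 30% to 70% as the range.

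**Formula.** Partial F test of one predictor added to k covariates: f² = R² / (1 − R²c − R²), where R² is the squared stated correlation; noncentrality λ = n·f²; degrees of freedom 1 and n − k − 2.

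**Step 1: reproduce Table 3** (k = 6). The column headed "Detectable Increase in R ²" comes out as follows.

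| n | computed | Table 3 | square root of computed | Table 3 R |
|---|---|---|---|---|
| 100 | 0.097 | 0.10 | 0.312 | 0.32 |
| 150 | 0.066 | 0.07 | 0.258 | 0.26 |
| 200 | 0.051 | 0.05 | 0.225 | 0.22 |
| 300 | 0.034 | 0.03 | 0.185 | 0.17 |
| 400 | 0.026 | 0.03 | 0.160 | 0.17 |
| 600 | 0.017 | 0.02 | 0.131 | 0.14 |

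The R² column reproduces to rounding. The R column is the square root of the rounded R², which is why n = 300 and n = 400 both show 0.17. At n = 300 this understates the detectable correlation.

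**Step 2: power at the stated R with the full n** (k = 6).
- EC: f² = 0.0676 / 0.8324 = 0.0812; λ = 150 × 0.0812 = 12.2; power 81%.
- EG: f² = 0.0289 / 0.8711 = 0.0332; λ = 300 × 0.0332 = 9.95; power 71%.
- EoE: f² = 0.0196 / 0.8804 = 0.0223; λ = 600 × 0.0223 = 13.4; power 86%.

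So EG falls short of 80% before any age split.

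**Step 3: power when one age group contributes** (adult/child dropped, k = 5).

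| Disease, R | n at 30 / 50 / 70% | power | R detectable at 80% power |
|---|---|---|---|
| EC, 0.26 | 45 / 75 / 105 | 23 / 43 / 62% | 0.45 / 0.36 / 0.31 |
| EG, 0.17 | 90 / 150 / 210 | 19 / 36 / 52% | 0.33 / 0.26 / 0.22 |
| EoE, 0.14 | 180 / 300 / 420 | 28 / 50 / 68% | 0.24 / 0.185 / 0.16 |

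With R²c = 0 the 50% powers are 38%, 31% and 44%. For EC at n = 75, raising R²c to 0.30 gives 57%. Reaching 80% power at R = 0.26 with one age-specific EC instrument takes about 148 patients of that age group, practically the whole EC sample.

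Whatever the split, the smaller age group holds at most half of the disease sample. For that group's instruments the 50% figures are therefore upper limits, given R²c = 0.10.

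**Step 4: estimability.** Take a single-age instrument and a design matrix with intercept, eosinophil count, adult/child indicator and their product. The indicator is constant, so it is a multiple of the intercept, and the product is a multiple of the eosinophil column. The rank is 2 of 4; neither age term can be estimated at any sample size.

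**The case against.** Section 12.3 calls the work exploratory, and section 12.4 foresees adult and paediatric subgroup analyses. Table 3 has rows at n = 100, 200 and 400, so a reader could look up a smaller sample; the EG value at n = 150 is simply the n = 150 row. This lowers the stakes but does not remove the error. Section 12.4 never applies the smaller rows to symptom or QoL scores, EC at n = 75 lies outside the table, and the 80% claim is attached explicitly to the disease totals.

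The size of the loss depends on an unstated age split and covariate R². That is correct, and it is why ranges are given. The direction does not depend on either.

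Several stronger readings are tempting, and the protocol does not support them:
- *Table 3 is wrong throughout.* It reproduces to rounding. The fault is which n is applied to which measure, plus the rounded EG entry.
- *The whole EG deficit comes from the age split.* Power at 0.17 is already about 71% at n = 300; the split takes it from there to 36%.
- *The interaction plan fails altogether.* The new-versus-established diagnosis interaction can be fitted for every COM, and the adult/child interaction for EREFS, Lanza and UCCIS. Section 12.5 does not formally define age group, and a term across paediatric age bands could be fitted within PEESS, though none is described.
- *The group effect size of 0.35 fails in the same way.* That sentence also covers outcomes not tied to age, and it carries no alpha of its own. Only PROMIS is a symptom or QoL measure shared by all three diseases. For EG versus EC at 150 versus 75, power at 0.35 is 45% at alpha 0.01 and 69% at 0.05.

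Scaling rules for combining instruments may be in an analysis plan that is not shown; their absence is not counted here. The n, the power, the one-model-per-COM rule and the age terms are all stated in the protocol itself.

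**Conclusion.** The concern holds for symptom and QoL measures. The power in section 12.4 is not a property of any of those analyses: at an even age split it is roughly 43% (EC), 36% (EG) and 50% (EoE) at the stated correlations, and it stays below 80% even with a 70% share in one age group. These figures assume a two-sided alpha of 0.01 and covariate R² of 0.10. Endoscopy and histology scores keep the full n, but the EG figure needs correcting for them too: the detectable R at n = 300 is about 0.185.

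With age group read as adults versus children, the age covariate and its interaction with eosinophil count are not estimable for any single symptom or QoL instrument. This needs no assumption about the split.

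**What to change.** 1. In section 12.4, limit the full-n figures to measures used at both ages. Correct the EG value from 0.17 to about 0.19. State the detectable correlation for each symptom and QoL measure from the expected paediatric and adult numbers. If the 0.35 effect size is meant to cover PROMIS, state its alpha and the n per form.
2. In section 12.5, drop the adult/child covariate and its interaction from single-age models, in the baseline and the one-year change analyses, and limit that interaction test to measures used at both ages.
3. Optionally, add a supportive model that standardises scores within instrument and combines the paediatric and adult scores of one disease, giving a pooled eosinophil association at the full n. Name the paediatric instrument in advance, since paediatric EG has PEESS child, PEESS parent and Likert. State that any slope difference by age is confounded with instrument; this model would not recover a clean age comparison.

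The cost is wording, less favourable stated figures and, if step 3 is taken, one extra analysis. Enrolment and data collection do not change.

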8.1 Screening

Subjects enrolled will have a confirmed diagnosis of EoE, EG or EC regardless of their treatment status as we are interested in the relationship between mucosal inflammation, whether currently present or not, with the COMs. Patients who are recruited will either have an established diagnosis of EoE, EG or EC and are undergoing SOC endoscopic analysis at the point of entry or will be patients who are undergoing endoscopy to establish a new diagnosis of EoE, EG or EC. *If EoE, EG, or EC diagnosis is new, enrollment and COM completion will occur within 4 weeks of the diagnostic endoscopy and prior to any treatments for their disease so that the impact of treatments will not impact any of the COMs.*

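### Section 12.4 calls 0.26, 0.17 and 0.14 true correlations, but they are square roots of an R² increase (semipartial correlations), so the 80% power claim does not carry over to the plain correlation

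*Protocol*

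**What the plan says.** Section 12.4 of the protocol sets the sizes: "We aim to enroll 600 EoE, 300 EG, and 150 EC patients in the trial between all participating sites". It then states: "This sample size will provide at least 80% power to detect a true correlation of 0.26 in the EC patients", continuing with "0.17 in the EG patients, and 0.14 in the EoE patients (Table 3". The alpha is 0.01, sidedness not given, and the calculation is made "when assuming an adjustment for 6 covariates within each disease (EoE, EG, EC".

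Table 3 has four columns: sample size, detectable increase in R², a corresponding R with covariate adjustment, and a correlation without adjustment. The row for 150 patients reads "150 0.07 0.26 0.27". For 300 the entries are 0.03, 0.17 and 0.20; for 600 they are 0.02, 0.14 and 0.14. The figures in the text are those of the adjusted column.

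Section 12.5 regresses each COM on peak eosinophil count: "Covariates in the model will include, but are not limited to, sex, age group, atopic disease, race, disease duration, and medication usage". Section 8.1 says: "Subjects enrolled will have a confirmed diagnosis of EoE, EG or EC regardless of their treatment status". New patients, by contrast, enrol and complete COMs before any treatment.

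**The concern.** The square root of an R² increase measures how much the eosinophil count adds once the covariates are in the model. A true correlation will be read as the plain association between COM and count, which is how Aim 1 is worded. The two generally agree only when the covariates carry no information about the count.

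That condition is doubtful here. Medication usage is in the model, treated and untreated patients are both enrolled, and section 4.2.1 (biopsy slide review) expects some biopsies to be inactive because of therapy.

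Table 3 is the power justification for the Aim 1 correlation analysis, and section 12.1 expects the analyses to help narrow down COMs for later composite scores. If sensitivity is overstated, a COM that does track the count may be set aside too readily.

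**Working it through.** **Inputs.** From section 12.4: N = 150 (EC), 300 (EG), 600 (EoE); alpha 0.01; 6 covariates; R = 0.26, 0.17, 0.14. Not in the protocol, so assumed: the share of COM variance explained by covariates (R²cov), and the share of eosinophil variance explained by covariates (q).

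**1. Table 3, unadjusted column.** Fisher z, two-sided alpha 0.01, 80% power gives 0.334, 0.275, 0.239, 0.196, 0.170 and 0.139 for N = 100, 150, 200, 300, 400 and 600. This matches the table, apart from 0.275 being shown as 0.27.

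**2. Table 3, R² column.** F test with 1 and N−8 df, noncentrality λ = N·ΔR²/(1 − R²cov − ΔR²).
- R²cov = 0.10: detectable gains 0.097, 0.066, 0.051, 0.034, 0.026, 0.017. All six round to the printed entries, and any R²cov of about 0.08 to 0.115 does the same.
- R²cov = 0: 0.108, 0.074, 0.056, 0.038, 0.029, 0.019. These do not match at N = 100, 200 and 300.

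So the table rests on an unstated R²cov of about 0.10.

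**3. Table 3, adjusted column.** √0.07 = 0.265, √0.03 = 0.173, √0.02 = 0.141. These are roots of the already rounded gains. Without rounding, at R²cov = 0.10, R is 0.258 (N = 150), 0.185 (N = 300) and 0.131 (N = 600). The rounding also explains why 0.17 appears for both 300 and 400 patients.

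**4. Power at the stated values, as semipartial correlations (ΔR² = R²).**

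| | λ at R²cov = 0.10 | Power | Power at R²cov = 0 |
|---|---|---|---|
| EC 0.26 | 150 × 0.0676 / 0.8324 = 12.18 | 80.9% | 75.3% |
| EG 0.17 | 300 × 0.0289 / 0.8711 = 9.95 | 71.3% | 65.4% |
| EoE 0.14 | 600 × 0.0196 / 0.8804 = 13.36 | 85.7% | 81.0% |

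**5. Power at the stated values, as plain correlations without adjustment.** Power = Φ(atanh(r)·√(N−3) − 2.576).
- EC: 0.2661 × 12.124 − 2.576 = 0.65, power 74%.
- EG: 0.1717 × 17.234 − 2.576 = 0.38, power 65%.
- EoE: 0.1409 × 24.434 − 2.576 = 0.87, power 81%.

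Table 3's own unadjusted entries (0.27, 0.20, 0.14) agree: 0.26 and 0.17 lie below the first two.

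**6. Overlap, illustration only.** Suppose covariates explain a share q of eosinophil variance and, to that extent, act on the COM only through the count, while other covariate effects explain 0.10 of COM variance. Then ΔR² = r²(1−q) and λ = N·r²(1−q)/(0.90 − r²). For EC at q = 0.2: 150 × 0.0541 / 0.8324 = 9.75.

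| q | EC, r = 0.26 | EoE, r = 0.14 |
|---|---|---|
| 0 | 81% | 86% |
| 0.1 | 76% | 81% |
| 0.2 | 70% | 75% |
| 0.33 | 60% | 66% |

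**7. The direction is not fixed.** Let a be the correlation of the count with a covariate composite (a² = q) and b that of the COM with the composite. Then ΔR² = (r − ab)²/(1 − a²). At q = 0.2:
- b = 0: ΔR² = 0.0676/0.8 = 0.0845 for EC (power about 86.5%) and 0.0196/0.8 = 0.0245 for EoE (90%).
- b = 0.2, same direction: ΔR² = 0.0364 for EC (43%) and 0.0032 for EoE (12%).

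**The case against.** The strongest reply is that nothing is miscalculated for EC and EoE. Table 3 heads the column as covariate-adjusted and prints the unadjusted correlation beside it. The R²-increase test is exactly the test of the eosinophil coefficient in the section 12.5 model, and its power for a given gain holds however strongly count and covariates are related. This stands: the EC and EoE rows reproduce when read as adjusted values, and it would be wrong to say that the power belongs to a model the study will not fit. What remains is the wording of the text, the undisclosed R²cov and the EG row.

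A reader might go further and infer that real power at 0.26 and 0.14 is some 55–75%. The documents do not support that. In the model of step 6 it would take a q of very roughly 0.1 to 0.45, and the protocol gives no q. It also assumes that the overlapping covariates affect the COM only through the count, and step 7 shows power moving either way once that is relaxed. The protocol leans towards treatment affecting COMs: section 8.1 wants COMs completed before treatment, and section 12.5 plans a mediation analysis. That makes some loss plausible but does not size it.

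It is also fair that section 12.3 calls the protocol more exploratory than validating, and that no rule reads a null result as evidence against a COM. This limits the consequence.

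**Conclusion.** The point holds as a mislabelled quantity with an undisclosed assumption. The stated values are semipartial correlations. The EC claim of 80% needs R²cov of about 0.10 (80.9%, against about 75% at zero). As plain unadjusted correlations, 0.26 and 0.17 fall short (about 74% and 65%), while 0.14 holds (81%). The EG value fails even as Table 3 labels it (about 71%), because R came from a gain rounded down from 0.034 to 0.03.

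These results assume a two-sided alpha of 0.01, which reproduces the unadjusted column. Overlap between medication and eosinophil count is likely from the entry rules, but its effect on power is illustrative only. Severity is moderate: the claim needs restating, but the design is not undermined.

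**What to change.** In section 12.4 and Table 3:
- Replace the term true correlation with semipartial correlation (square root of the R² increase).
- State the assumed R²cov and the sidedness of alpha.
- Beside the existing unadjusted column, give the detectable plain correlation over a range of q, for example 0 to 0.4, with the model behind it. Dividing the unrounded R by √(1−q) gives, at q = 0.4, about 0.258/0.775 = 0.33 (EC), 0.185/0.775 = 0.24 (EG) and 0.131/0.775 = 0.17 (EoE). This is an approximation under step 6.
- Derive R from unrounded gains, so that EG at 300 patients reads about 0.185.

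The cost is wording and one recalculated table. The stated detectable correlations become slightly less favourable overall, and no patients are added.
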